7.2.1 Progression-Free Survival

Progression-free survival (PFS) is defined as the duration of time from start of treatment until objective tumor progression or death.

8.0 ADVERSE EVENTS

An adverse event (AE) is any untoward medical occurrence in a patient receiving study treatment and which does not necessarily have a causal relationship with this treatment. An AE can therefore be any unfavorable and unintended sign (including an abnormal laboratory finding), symptom, or disease temporally associated with the use of an

experimental intervention, whether or not related to the intervention.

8.1 Adverse Event Monitoring

Adverse event data collection and reporting, which are required as part of every clinical trial, are done to ensure the safety of subjects enrolled in the studies as well as those who will enroll in future studies using similar agents. Adverse events are reported in a routine manner at scheduled times during a trial. Additionally, certain adverse events must be reported in an expedited manner to allow for optimal monitoring of patient safety and care.

As far as possible, each adverse event should be evaluated to determine:

- duration (start and end dates)
- severity (grade)
- seriousness
- relationship to study agent
- action taken (i.e., none, study agent modification, medical intervention)
- outcome (i.e., resolved without sequelae, resolved with sequelae, ongoing)

All patients experiencing an adverse event, regardless of its relationship to study drug, will be monitored until:

- the adverse event resolves or the symptoms or signs that constitute the adverse event return to baseline;
- any abnormal laboratory values have returned to baseline;
- there is a satisfactory explanation other than the study drug for the changes observed; or
- death.

8.2 Severity

All non-hematologic adverse events will be graded according to the NCI Common Terminology Criteria for Adverse Events (CTCAE) version 4.03. The CTCAE v4.03 is available at http://ctep.cancer.gov/reporting/ctc.html. All hematologic adverse events will be graded according to the modified iwCLL criteria.

If no grading is available, the severity of an AE is graded as follows:

Mild (grade 1): the event causes discomfort without disruption of normal daily activities.

Moderate (grade 2): the event causes discomfort that affects normal daily activities.

Severe (grade 3): the event makes the patient unable to perform normal daily activities or significantly affects his/her clinical status.

Life-threatening (grade 4): the patient was at risk of death at the time of the event.

Fatal (grade 5): the event caused death.

8.3 Seriousness

A "serious" adverse event is defined in regulatory terminology as any untoward medical

occurrence that:

- Results in death.
 - If death results from (progression of) the disease, the disease should be reported as event (SAE) itself.
- 2. Is life-threatening.
 - (the patient was at risk of death at the time of the event; it does not refer to an event that hypothetically might have caused death if it were more severe).
- 3. Requires in-patient hospitalization or prolongation of existing hospitalization for ≥ 24 hours.
- 4. Results in persistent or significant disability or incapacity.
- 5. Is a congenital anomaly/birth defect
- 6. Is an important medical event

Any event that does not meet the above criteria, but that in the judgment of the investigator jeopardizes the patient, may be considered for reporting as a serious adverse event. The event may require medical or surgical intervention to prevent one of the outcomes listed in the definition of "Serious Adverse Event".

For example: allergic bronchospasm requiring intensive treatment in an emergency room or at home; convulsions that may not result in hospitalization; development of drug abuse or drug dependency.

8.4 Relationship

Attribution categories for adverse events in relationship to protocol therapy are as follows:

Definite – The AE *is clearly related* to the study treatment.

Probable – The AE *is likely related* to the study treatment.

Possible – The AE *may be related* to the study treatment.

Unlikely – The AE *is doubtfully related* to the study treatment.

Unrelated – The AE *is clearly NOT related* to the study treatment.

8.5 Prior experience

Expected events are those that have been previously identified as resulting from administration of the agent. An adverse event is considered unexpected, for expedited reporting purposes only, when either the type of event or the severity of the event is not listed in the toxicities listed in the agent information section of this protocol.

8.6 Reporting Requirements for Adverse Events

8.6.1 Expedited Reporting

- The Principal Investigator must be notified within 24 hours of learning of any serious adverse events, regardless of attribution, occurring during the study or within 30 days of the last administration of the study drug.
- The UCSD Human Research Protections Program (HRPP) must be notified within 10 business days of "any unanticipated problems involving risk to subjects or others" (UPR).

The following events meet the definition of UPR:

- 1. Any serious event (injuries, side effects, deaths or other problems), which in the opinion of the Principal Investigator was unanticipated, involved risk to subjects or others, and was possibly related to the research procedures.
- 2. Any serious accidental or unintentional change to the IRB-approved protocol that alters the level of risk.
- 3. Any deviation from the protocol taken without prior IRB review to eliminate apparent immediate hazard to a research subject.
- 4. Any new information (e.g., publication, safety monitoring report, updated sponsor safety report), interim result or other finding that indicates an unexpected change to the risk/benefit ratio for the research.
- 5. Any breach in confidentiality that may involve risk to the subject or others.
- 6. Any complaint of a subject that indicates an unanticipated risk or that cannot be resolved by the Principal Investigator.
- The FDA should be notified within 7 calendar days of any unexpected fatal or life-threatening adverse event with possible relationship to study drug, and 15 calendar days of any adverse event that is considered: 1) serious, 2) unexpected, and 3) at least possibly related to study participation.

8.6.2 Routine Reporting Requirements

- The UCSD HRPP will be notified of any adverse events that are not unanticipated problems involving risk to subjects or others (non-UPRs) at the time of the annual Continuing Review.
- The FDA will be notified of all non-serious adverse events annually at the time of the annual report.

9.0 AGENT INFORMATION

9.1 UC-961 (Cirmtuzumab)

Please refer to Investigator's Brochure for more comprehensive information.

Structure: Monoclonal antibody

Supplied by: UC-961 will be produced at Pacific GMP (San Diego, CA) in compliance with cGMP standards.

Formulation

The agent is supplied as a liquid formulation at a concentration of 40 mg/ml protein, with 7.2 to 7.8 mL/vial. Each ml of the formulation contains 40 mg UC-961, 14.7 mg sodium citrate, 10 mg trehalose, 216 μ g Polysorbate 80, 15 μ g sodium EDTA and adjusted to pH 5.2 \pm 0.2.

UC-961 will be filled into 10ml clear borosilicate Type 1 glass vials with 20 mm grey butyl siliconized rubber stopper and 20 mm aluminum royal blue flip off seals.

Storage

UC-961 is to be kept refrigerated (2-8°C) until use, in single use vials.

Solution Preparation

To prepare the agent for administration, it will be dissolved in normal saline to the following final concentrations:

- 100 μg/mL for doses 15 μg/kg to 240 μg/kg
- 500 μg/mL for doses 500 μg/kg to 2 mg/kg
- 1 mg/mL dose 4 mg/kg
- 2 mg/mL for dose 8 mg/kg
- 4 mg/mL for doses 16mg/kg and 20 mg/kg

Administration

The drug will be administered by intravenous infusion with infusion rate according to section 4.4.

Toxicities and tolerability

No toxicities have been yet identified in the ongoing first-in-man study. The agent has been well tolerated. There is no off-target binding identified in initial preclinical assays. Infusion reaction, fluid retention, tumor lysis syndrome, and immunogenicity are possible class effects of monoclonal antibody therapy. Depletion of precursor B cells and B cell lymphopenia are possible as well. Other ROR1 antibodies, distinct from UC-961, have demonstrated binding to pancreatic islet cells and adipose tissue (Hudecek et al., 2010). Glucose levels and body weight will therefore be monitored.

10.0 STATISTICAL CONSIDERATIONS

The primary aim of the study is to determine the safety of UC-961 therapy given at the currently used, biologically active dose, or RP2D for an extended duration.

Safety will be assessed through summaries of adverse events, clinical laboratory abnormalities, and changes in physical exam and vital signs. All subjects who receive a single dose of study medication will be considered evaluable for safety.

Adverse events will be listed, documenting the course, outcome, severity, and relationship to the study treatment. Incidence rates of AEs and the proportion of subjects prematurely withdrawn from the study due to AEs will be shown.

The primary endpoint of this study is the rate of dose-limiting toxicity (DLT).

SECONDARY ANALYSIS

Secondary Endpoints are overall response rate by IWCLL criteria following 6 months of biweekly dosing of UC-961 (Hallek *et al.*, 2008); Progression free and overall survival (progression determined by IWCLL working group criteria); and SD, PR, and MRD-rates, as well as individual components of response (reduction in leukemia count, reduction in adenopathy and splenomegaly, and improvement in BM function), as determined by IWCLL working group criteria.

These secondary endpoints will be summarized by dose cohort, clinical characteristics and overall using percentages, means and median survival estimates as appropriate. Data will also be presented graphically with Kaplan Meier plots, box plots, and bar charts. All statistics will be presented with 95% confidence intervals. The analysis will be descriptive; thus no correction for multiple analyses will be made and no formal tests of hypothesis will be done.

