1.4 Rationale for Dose Selection

Each extension course consists of 8 infusions. A patient may repeat the course, and therefore receive a total of 16 infusions on the extension study. Each individual patient will receive the same

dosage of UC-961 for each of the 8 infusions of each course. The dosage of UC-961 may be increased for the 2nd set of 8 infusions (if a higher dose has been shown to be safe on the phase 1 trial AND there is Progressive Disease or Stable Disease after the first course of extension.

The dose administered on this extension study will be the highest safe dose, or once established, the biologically active dose or the recommended phase 2 dose from the phase 1 trial. To date, the 8 mg/kg dose level has been completed and determined to be safe. Therefore, patients on this extension study will begin at the 8 mg/kg dose level. Should subsequent dose levels be determined to be safe in the Phase 1 trial, the dose utilized in this trial may increase for subsequent patients.

Planned dose levels (starting dose is the highest safe dose administered to a patient in the phase 1 trial):

Potential	Dose		
Dose Level			
-1	4 mg/kg		
1 (start)	8 mg/kg		
2	16 mg/kg (or max 2000 mg dose)		
3	20 mg/kg (or max 2000 mg dose)		

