2.4 Primary Endpoint

2.4.1 Safety and tolerability with extended dosing of UC-961 based on ongoing evaluation of AEs during treatment and 3 month follow up

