4.2 Dose Limiting Toxicity

Dose-Limiting Toxicity (DLT) is defined as any of the following adverse events that are considered by the investigator to be possibly, probably, or definitely related to the study agent UC-961 within the 28 days of the start investigational treatment:

- CTCAE Grade 3 or higher non-hematologic toxicity, except for: Grade 3 infections lasting < 7 days that have resolved, or one occurrence of Grade 3 infusion reaction; or
- Grade 4 or higher hematologic toxicity (by modified iwCLL criteria); or
- Any AE requiring a dose delay of greater than 28 days;

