4.5 Criteria for dosing

Doses are administered on day 1, 15, 29, 43, 57, 85, 113, and 141 (+/-3 days) if the patient is without ongoing Grade 3 non-hematologic or Grade 4 hematologic toxicities attributable to UC-961.

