7.1 Safety/tolerability

7.1.1 Common Terminology Criteria for Adverse Events (CTCAE)

Analyses will be performed for all patients having received at least one dose of study drug. The study will use the CTCAE version 4.03 (http://ctep.cancer.gov/reporting/ctc.html) for reporting of non-hematologic adverse events.

7.1.2 International Working group for Chronic Lymphocytic Leukemia (IWCLL) criteria for hematologic toxicity

As is the case with virtually all of the hematological malignancies, an evaluation of the hematological toxicity in patients with CLL must consider the high frequency of marrow involvement and consequent medullar compromise at the initiation of therapy. A substantial proportion of patients will have hematological parameters within the range of Grade 2-4 hematological toxicity before therapy is given; therefore, a modified schema will be used to monitor hematological toxicity in patients with CLL. The modified hematological toxicity schema is displayed:

Modified Grading Scale for Hematological Toxicity in CLL Studies			
Grade ¹	Decrease in platelets (nadir) from pretreatment value (%) ²	ANC/μI (nadir)³	Hemoglobin ⁴
0 (not AE)	10%, or above lower limit of normal for institution.	≥ 1800, or above lower limit of normal for institution.	Baseline or higher, or above lower limit of normal for institution.
1	11-24%	≥ 1500 and < 1800	> 10.0 g/dL and below baseline
2	25-49%	≥ 1000 and < 1500	< 10.0 – 8.0 g/dL and less than baseline
3	50-74%	≥ 500 and < 1000	< 8.0 – 6.5 g/dL and less than baseline
4	≥75% or ≤ 25,000/mm3 ²	< 500	< 6.5 g/dL and less than baseline

^{*}This schema concurs with the CTEP CTCAE 4.03, except for the platelet values are taken from the iwCLL-WG guidelines working group criteria and hemoglobin toxicity modified from CTCAE only to account for low baseline values in CLL patients. No hematologic toxicity will be registered unless hemoglobin falls below baseline level.

¹ Grades: 1, mild; 2, moderate; 3, severe; 4, life threatening; 5, fatal. Death occurring as a result of toxicity at any level of decrease from pretreatment will be recorded as a Grade 5.

² Treatment will be held for platelet count ≤ 25,000/mm3, even if it does not meet grade 4 criteria based on percent decrease. See section 4.6.1 for dose hold/adjustment guidelines.

³ If baseline ANC is <1,500/μL, neutrophil toxicity cannot be evaluated. In that case, if

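### AE incidence in section 10 is undefined and pooled over all exposure, so the plan has no summary that can show how risk changes with longer dosing or after a dose change

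*Combined protocol and SAP*

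**What the plan says.** Section 2.4.1 defines the primary endpoint as "Safety and tolerability with extended dosing of UC-961 based on ongoing evaluation of AEs during treatment and 3 month follow up". Section 10 repeats the extended-duration aim but then names the DLT rate as the primary endpoint. Section 4.2 counts a DLT only if it occurs "within the 28 days of the start investigational treatment".

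The AE analysis in section 10 has three parts: summaries and listings, the statement that "Incidence rates of AEs and the proportion of subjects prematurely withdrawn from the study due to AEs will be shown", and the analysis set: "All subjects who receive a single dose of study medication will be considered evaluable for safety". Section 7.1.1 gives the same set. Dose-cohort summaries, Kaplan-Meier plots and 95% confidence intervals appear only in the paragraph on secondary endpoints.

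On exposure, section 1.4 states: "A patient may repeat the course, and therefore receive a total of 16 infusions on the extension study". Dose may differ between patients and between courses (sections 1.4 and 4.1) and may be reduced for toxicity (section 4.6.1). After treatment stops, visits with AE grading continue every 28 days for 8 visits and then every 56 days. They end at death, loss to follow-up, withdrawal of consent or subsequent therapy for progression (sections 4.10 and 5.5).

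**The concern.** A patient who stops after one infusion and a patient who receives 16 enter the same denominator. A single pooled figure over such a mixture describes treated patients on average. It does not describe the risk of staying on treatment, which is what the trial sets out to learn.

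The DLT rate cannot fill the gap, because its window closes before most of the dosing takes place. Later toxicity therefore rests on the AE summary, whose measure is not defined and which is not broken down by time or dose. At stake are two readings: whether risk is higher in Course 2 than in Course 1, and whether it changes after a dose increase. The design allows both situations, and the plan has no table for either.

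**Working it through.** The plan states no AE rate, dropout rate or precision for safety, so there is no figure of its own to reproduce. Every risk and leaving rate below is an assumption. Days 169 and 365 (response assessments, section 6.0), 28 days (section 4.2), 33 patients (synopsis) and 8 visits × 28 = 224 days (section 4.10) come from the documents.

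**1. Reach of the DLT rate.** 28/169 = 16.6% of the time to the first response assessment and 28/365 = 7.7% of the two-course schedule. Nominally it spans the infusions on days 1 and 15.

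**2. Risk confined to Course 2.** Pooled proportion = R × s, where R is the risk among those who reach Course 2 and s is the fraction who do. With R = 20%:

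| s | Pooled figure |
|---|---|
| 80% | 16% |
| 60% | 12% |
| 40% | 8% |

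**3. Constant hazard, leaving unrelated to AEs, no AE capture after leaving.** Let R be the risk over full exposure T and D the fraction who leave by T. Then λ = −ln(1−R)/T, μ = −ln(1−D)/T, and the pooled proportion is λ/(λ+μ) × [1 − (1−R)(1−D)]; T cancels. With R = 20% and D = 50%: 0.2231/(0.2231+0.6931) × (1 − 0.8×0.5) = 0.2435 × 0.6 = 14.6%. The same formula gives 19.0% at D = 10%, 16.9% at 30% and 11.9% at 70%, a relative shortfall of 5% to 41%.

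**4. What shrinks or removes the shortfall** (R = 20%, D = 50%, T = 169, so λ = 0.00132 and μ = 0.00410 per day).
- AE capture for f days after leaving, hazard unchanged: (1−e^(−μ(T−f))) − e^(−λf) × μ/(λ+μ) × (1−e^(−(λ+μ)(T−f))) + R × e^(−μ(T−f)). This gives 16.3% for f = 30 and 18.7% for f = 90. With f = 224 every leaver is observed past day 169, so the result is 20.0%.
- Leaving caused only by the AE itself: the event is counted first, so 20.0%.
- All risk in the first 28 days: λ = 0.2231/28 = 0.00797; 0.00797/(0.00797+0.00410) × (1 − e^(−0.01207×28)) = 18.9%.

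**5. Precision hidden by pooling.** With zero events, the exact two-sided 95% upper limit is 1 − 0.025^(1/n): 10.6% for n = 33, but 19.5% if only 17 patients reach the later doses.

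**6. Does an exposure-adjusted rate help?** In a simulation of 400,000 patients under the step 3 assumptions (R = 20%, D = 50%), the pooled proportion was 14.7%. Events divided by person-time, converted back to a risk over T, gave 20.1%. This holds under a constant hazard. If the hazard changes over time, the rate must be split by period.

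**The case against.** A reader might go further and infer that the plan commits to a crude proportion, that this is the primary analysis, and that it is biased low by a large amount. One could illustrate this with 5% risk per 28 days over 13 periods and 40% of patients leaving after two periods. The full risk is 1 − 0.95^13 = 48.7%, and the pooled figure is 0.6 × 48.7% + 0.4 × (1 − 0.95^2) = 33.1%. At 2% per period the pair is 23.1% and 15.4%.

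The documents do not support that reading, for four reasons.
- Section 10 uses proportion for withdrawals and incidence rates for AEs, and leaves the latter undefined.
- The endpoint it calls primary is the DLT rate, which a departure at day 56 cannot dilute.
- Those figures stop AE capture at departure, whereas sections 4.10 and 5.5 continue it. Giving early leavers three more periods at an unchanged hazard yields 0.6 × 48.7% + 0.4 × (1 − 0.95^5) = 38.2%; eight more yield 0.6 × 48.7% + 0.4 × (1 − 0.95^10) = 45.2%. At 2% the corresponding values are 17.7% and 21.2%.
- The low bias needs exits unrelated to AEs and risk that comes late. Neither can be read from the plan.

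It is also fair to say that an at-least-one-dose safety set is standard, that withdrawals for AEs are reported separately, that individual AE listings let a reader inspect timing, and that about 33 patients will not support fine subdivision.

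These points remove the claim of a fixed, large bias, but the gap remains. Off-treatment visits do not stand in for Course 2 infusions, and they end at subsequent therapy for progression. Listings are not estimates. And even if nobody left early, one pooled figure could not separate periods or doses.

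**Conclusion.** The point holds as a gap in specification. The AE incidence measure is undefined, and no AE summary by treatment period or dose is planned, although the aim is extended-duration safety and exposure and dose both vary. If the measure is a pooled per-patient proportion, it cannot answer the extended-dosing question. It may also be low for long exposure when exits are unrelated to AEs, risk is late and follow-up is cut short by new therapy.

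The size cannot be taken from the documents. Under the assumptions shown it ranges from nothing (exits caused by the AE, or full follow-up at an unchanged hazard) to showing 8% for a 20% Course 2 risk when 40% of patients reach that course. Separately, sections 10 and 2.4.1 name different primary endpoints, and the one in section 10 does not measure extended dosing. The plan should be changed, but the at-least-one-dose analysis set is not an error.

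**What to change.** 1. Keep the at-least-one-dose AE table, and state whether incidence is patients with an event over patients treated or events per person-time.
2. Add AE incidence with numbers at risk and person-time by period: first 28 days, rest of Course 1, Course 2, and 3-month follow-up.
3. Add the same summary by dose at onset, as a separate table rather than crossed with period. Read it descriptively: a higher Course 2 dose goes to patients with stable or progressive disease, so dose groups are not comparable.
4. Add cumulative incidence of first Grade 3 or higher AE, with death and new therapy as competing events.
5. Give 95% confidence intervals for all of these.
6. Reconcile the primary endpoint in section 10 with section 2.4.1.

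No new data are needed: AE start and end dates (section 8.1) and drug administration times (sections 5.6 and 5.7.1) are already to be recorded. The cost is one or two extra descriptive tables, with sparse cells and wide intervals at about 33 patients.

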4.6 Dose Modifications and Dosing Delays

Each patient will be assessed for the development of toxicity according to the NCI Common Toxicity Criteria for Adverse Events (CTCAE), version 4.03 for non-hematologic toxicity or modified iwCLL criteria (section 7.1.2) for hematologic toxicity. Patients experiencing a DLT as defined in section 4.2 will be discontinued from study treatment. Otherwise, dose adjustments should be made according to the system showing the greatest degree of toxicity, as per 4.6.1, unless the adverse event is definitely unrelated to the study drug. Dose levels are listed in section 1.4.

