- 2. UC-961 infusions can be delayed for a maximum of 28 days; if not restarted in that timespan, study treatment will be permanently discontinued.

- 3. If dose is decreased for Grade 3 or 4 toxicity, dose re-escalation is not planned.
- 4. For invasive procedures, not including biopsies or venous catheter placement: withhold study treatment for 1 week prior to procedure, and at least 1 week following surgery until satisfactory wound healing has been achieved.

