4.10 Duration of Follow Up

Patients removed from study treatment for unacceptable adverse events will be followed until resolution or stabilization of the adverse event. Patients will be followed after removal from study treatment every 28 days (+/-7 days) for 8 visits, then every 56 days (+/- 7 days) until death, lost to follow-up, withdrawal of consent, or initiation of subsequent therapy for disease progression (see Section 5 for assessments).

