4.11 Criteria for Removal from Study

Patients can be taken off the study at any time at their own request, or they may be withdrawn at the discretion of the investigator for safety, behavioral or administrative reasons. The reason(s) for discontinuation will be documented and may include:

- a) Death.
- b) Loss to follow-up.
- c) Withdrawal of consent for any further data submission.
- d) Disease progression requiring initiation of subsequent therapy.

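### Section 10's only discontinuation statistic counts withdrawal from the study for AEs, not stopping UC-961 for AEs, so toxicity stops after day 28 or below DLT grade can go uncounted

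*Combined protocol and SAP*

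**What the plan says.** Section 2.4 gives the primary endpoint as "Safety and tolerability with extended dosing of UC-961 based on ongoing evaluation of AEs during treatment and 3 month follow up". Section 10 plans AE listings and incidence rates, summaries of laboratory, physical-examination and vital-sign findings, and this discontinuation figure: "the proportion of subjects prematurely withdrawn from the study due to AEs will be shown". It then adds: "The primary endpoint of this study is the rate of dose-limiting toxicity (DLT)". It plans no proportion of patients who stop UC-961 because of an AE.

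The treatment sections act on study treatment:

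- Section 4.6: "Patients experiencing a DLT as defined in section 4.2 will be discontinued from study treatment".
- Section 4.6.1 stops therapy for specified repeat toxicities. For an infusion delayed beyond the 28-day maximum it says: "if not restarted in that timespan, study treatment will be permanently discontinued".
- Section 4.6.2 stops study treatment after a second Grade 3 infusion reaction or any Grade 4 reaction.

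Section 4.10 then says: "Patients removed from study treatment for unacceptable adverse events will be followed until resolution or stabilization of the adverse event". It also sets a visit schedule after removal from treatment, which ends only at death, loss to follow-up, consent withdrawal or new therapy for progression. The four reasons itemised in Section 4.11 for leaving the study match these (the last is "Disease progression requiring initiation of subsequent therapy"), and an AE is not among them.

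**The concern.** Stopping the drug and leaving the study are different events under this protocol. Tolerability of extended dosing is about the first: how many patients could not continue UC-961 because of toxicity. Section 10 tabulates the second. If the final tables follow the text literally, a patient who stopped UC-961 for toxicity and attended every follow-up visit adds nothing to the only discontinuation figure. If site staff treat a treatment stop as a removal from study, the same patient is counted. A reader of the report could not tell which convention was used, and under the literal one a low percentage would look like good tolerability.

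**Working it through.** Section 10 gives no figure to reproduce. The analysis is descriptive, and the anticipated enrolment of 33 (up to 75) has no statistical derivation. The check is a comparison of the texts, a count of doses inside the DLT window, and an illustration of size.

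**1. Is a patient who stops UC-961 for an AE withdrawn from the study?**

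| Place | What ends for an AE | What follows |
|---|---|---|
| 4.6, 4.6.1, 4.6.2, 4.9 | Study treatment | Not addressed there |
| 4.10 | Study treatment | Follow-up continues |
| 4.11, itemised reasons | Study; no AE item | – |
| 4.11, lead sentence | Study, at investigator discretion, including for safety | – |
| Synopsis, first duration list | AEs given as a reason for removal from study | – |
| Synopsis, second list (end of participation and long-term follow-up) | No AE item | – |

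Under 4.10 and the itemised reasons in 4.11 the answer is no. Under the first synopsis list, or the discretionary route in 4.11, it can be yes.

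**2. Does the DLT rate fill the gap?** Section 4.2 limits DLTs to related events "within the 28 days of the start investigational treatment". Course 1 doses fall on days 1, 15, 29, 43, 57, 85, 113 and 141.

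- Doses by day 28: days 1 and 15, so 2 of 8. If day 29 counts, 3 of 8.
- Over both courses (16 doses): 2 or 3 of 16.
- Time to the first response assessment: 28/169 = 17%. Time to the second: 28/365 = 8%.

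A stop after the window is outside the DLT rate whatever its grade.

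**3. Are all stops inside the window DLTs?** No. For non-hematologic toxicity Section 4.2 starts at Grade 3. Section 4.6.1 discontinues therapy on a repeat of Grade 2 or higher confusion or delirium, pneumonitis or acute kidney injury. A repeat Grade 2 event of these types stops UC-961 without being a DLT by grade, even in the first month. It would be one only through the separate criterion of a dose delay over 28 days.

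**4. Do the AE tables fill the gap?** Incidence rates show that events occurred, not that patients had to stop. The AE listing in Section 10 covers course, outcome, severity and relationship. Action taken is evaluated under Section 8.1 but is not named for that listing, and its categories do not separate permanent discontinuation from a reduction or a hold.

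**5. Size, with assumed counts.** The documents give no discontinuation rate. Suppose k patients out of n stop UC-961 for toxicity after day 28 and all stay in follow-up. The literal statistic is 0/n and the treatment-discontinuation proportion is k/n. Exact (Clopper-Pearson) 95% limits are: lower = Beta(0.025; k, n−k+1), upper = Beta(0.975; k+1, n−k). For k = 0 the lower limit is 0 and the upper is 1 − 0.025^(1/n).

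| n | k (assumed) | Literal study-withdrawal figure | Stopped UC-961 for AEs |
|---|---|---|---|
| 33 | 3 | 0% (0 to 10.6%) | 9.1% (1.9 to 24.3%) |
| 33 | 6 | 0% (0 to 10.6%) | 18.2% (7.0 to 35.5%) |
| 75 | 15 | 0% (0 to 4.8%) | 20.0% (11.6 to 30.8%) |

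Check for n = 33, k = 0: 1 − 0.025^(1/33) = 0.106.

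**The case against.** The strongest reply is that Section 10 does not rest on this one number. It names the DLT rate as the primary endpoint, and by Section 4.6 every DLT is a treatment stop. It also reports AE incidence and lists every AE, and under Section 11.4 the DSMB sees all AEs regardless of grade and attribution. This stands. A reader might infer that the withdrawal proportion is the plan's only tolerability statistic; it is only the sole discontinuation statistic. A DLT, a second Grade 3 infusion reaction and an AE delay of more than 28 days are all DLT event types, and the DLT rate counts them when they are related and fall in the first 28 days.

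The second reply is that the withdrawal phrase may simply mean stopping protocol therapy. The first synopsis list gives AEs as grounds for removal from study and is separate from the list that ends follow-up. Section 4.8 likewise removes from study a patient given prohibited therapy. Section 4.11 introduces its reasons as examples and permits withdrawal for safety. This also stands as far as it goes. A reader might infer that the figure must come out near zero, but the documents make that possible, not certain. The reply does not rescue the statistic, because it shows two defensible readings that give different numbers for the same patients.

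Finally, the analysis is descriptive, so no test is distorted, and AEs themselves are not concealed. What goes unreported is how many patients they stopped.

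**Conclusion.** The concern holds in limited form. Section 10 has no statistic that reliably counts patients who stop UC-961 for toxicity after day 28, or for events below DLT grade. Its only discontinuation figure depends on which passage is used to interpret the word study. For a trial whose primary objective is safety and tolerability of extended dosing, this is worth correcting before the tables are produced.

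The contrast of 0/33 with 6/33 = 18.2% is an illustration, not an estimate. It assumes six toxicity stops, all after day 28, all remaining in follow-up, and a literal reading of the statistic. Early stops that meet the DLT definition are reported through the DLT rate. The documents do not support saying that toxicity will be hidden or that a near-zero figure is inevitable.

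**What to change.** 1. In Section 10, report the proportion of treated patients who permanently discontinue UC-961 due to AEs, with a 95% CI. Keep withdrawal from the study due to AEs as a separate disposition line.
2. In the action-taken item of Section 8.1, record permanent discontinuation separately from dose reduction and delay.
3. Reconcile the terms *study* and *study treatment* across the synopsis section on duration and participation, Sections 4.10 and 4.11, and Section 10.

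Summaries of AE-related reductions, of delayed or omitted infusions, and of infusions given over planned would help but are optional. No dosing or stopping rule changes. The cost is one sentence, one table row and one data category, plus the wording reconciliation.
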